  - a. **Table 4**, use a 2 x 2 table to determine the agreement hypertension on ABPM and clinic BP (i.e., HYP\_AB\_ATTEND versus HYP\_AB\_UNATTEND); provide the p-value from kappa statistics.
  - b. **Table 5**, use a 2 x 2 table to determine the agreement white coat hypertension on ABPM and clinic BP (i.e., WHIT\_AB\_ATTEND versus WHIT\_AB\_UNATTEND); provide the p-value from kappa statistics.
  - c. **Table 6**, use a 2 x 2 table to determine the agreement masked hypertension on ABPM and clinic BP (i.e., WHIT\_AB\_ATTEND versus WHIT\_AB\_UNATTEND); provide the p-value from kappa statistics.
5. Do the following analysis for **Table 7** for those with complete sleep BP data on ABPM and HBPM:
  - a. For sleep systolic BP, calculate the mean BP (with standard deviation) on ABPM and HBPM.
  - b. Calculate the absolute mean difference with 95% confidence intervals for ABPM vs. HBPM, using a paired T-test.
  - c. Repeat items 5a and 5b for sleep diastolic BP on ABPM and HBPM.
6. **Table 8**. Calculate the number and percentage of side effects and tolerability (**listed in Table 8**) that occurred in ABPM only, HBPM only, both ABPM and HBPM, and occurred for neither ABPM nor HBPM.
7. **Table 9**. Restrict the analysis to those with complete data on attended and unattended BP and complete data on left ventricular mass index .
  - a. Use linear regression to determine the relationship between attended SBP with left ventricular mass index.
  - b. Repeat the analysis for attended DBP, unattended SBP, unattended DBP with left ventricular mass index, separately.

8. **Table 10.** Restrict the analysis to those with complete BP data on unattended and awake ABPM and complete data on left ventricular mass index.
  - a. Use linear regression to determine the relationship between unattended SBP with left ventricular mass index.
  - b. Repeat the analysis for unattended DBP, awake SBP on ABPM, awake DBP on ABPM with left ventricular mass index, separately.
9. **Table 11.** Restrict the analysis to those with complete sleep BP data on ABPM and HBPM and complete data on left ventricular mass index.
  - c. Use linear regression to determine the relationship between sleep SBP on ABPM with left ventricular mass index.
  - d. Repeat the analysis for sleep DBP on ABPM, sleep SBP on HBPM, and sleep DBP on HBPM with left ventricular mass index, separately.

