Unattended: SBP/DBP readings  $\geq$ 135 or 85 mm Hg

**Table 4.** Agreement between hypertension on ABPM and clinic BP, N=569

		ABPM and unattended clinic BP in hypertensive range		N (%)
		Yes, %	No, %	
ABPM and attended clinic BP in hypertensive range	Yes, %	25 (4.4)	1 (0.2)	26 (4.6)
	No, %	14 (2.5)	529 (93.0)	543 (95.4)
	N (%)	39 (6.9)	530 (93.2)	569 (100)
Kappa: 0.76				

**Table 5.** Agreement between white coat hypertension on ABPM and clinic BP, N

		Hypertensive unattended clinic BP with normal ABPM		
		Yes, %	No, %	N (%)
Hypertensive attended clinic BP with normal ABPM	Yes, %	15 (2.6)	0 (0.0)	15 (2.6)
	No, %	26 (4.6)	528 (92.8)	554 (97.4)
N (%)		41(7.2)	528 (92.8)	569 (100)

Kappa: 0.52

**Table 6.** Agreement between masked hypertension on ABPM and clinic BP, N

		Hypertensive ABPM with normal unattended clinic BP		
		Yes, %	No, %	N (%)
Hypertensive ABPM with normal attended clinic BP	Yes, %	17 (3.0)	14 (2.5)	31 (5.5)
	No, %	1 (0.2)	537 (94.4)	538 (94.6)
N (%)		18 (3.2)	551 (96.8)	569 (100)
Kappa: 0.68				

**Table 7.** The difference between sleep BP on HBPM versus sleep BP on ABPM, N = 547

	ABPM Mean (SD) Median, (min – max)	HBPM Mean (SD) Median (min – max)	Mean difference, (95% CI)	P (difference = 0)
Sleep systolic BP	104.1 (10.5) 103.3 (72.3 - 145.0)	106.4 (11.5) 106.0 (74.0 - 159.0)	-2.3 (-3.0, -1.5)	<.0001
Sleep diastolic BP	60.4 (7.5) 59.8 (42.1 - 95.4)	62.3 (8.3) 62.0 (38.0 - 88.0)	-1.9 (-2.5,-1.4)	<.0001

**Table 8.** Side effects and tolerability of HBPM versus ABPM, N = 603.

	Occurred with ABPM only, N (%)	Occurred with HBPM only, N (%)	Occurred with both ABPM and HBPM, N (%)	Didn't occur for ABPM or HBPM, N (%)
Side effects				
Pain while wearing the monitor	160 (26.5)	37 (6.1)	128 (21.2)	278 (46.1)
Irritation while wearing the monitor	178 (29.5)	26 (4.3)	232 (38.5)	167 (27.7)
Bruising while wearing the monitor	84 (13.9)	19 (3.2)	54 (9.0)	446 (74.0)
Tolerability				
Monitor was heavy to wear	133 (22.1)	57 (9.5)	139 (23.1)	274 (45.4)
Monitor was uncomfortable to wear	109 (18.1)	68 (11.3)	399 (66.2)	27 (4.5)
Monitor was straightforward to use	12 (2.0)	6 (1.0)	578 (95.9)	7 (1.2)
Monitor was cumbersome or awkward to wear	130 (21.6)	27 (4.5)	377 (62.5)	69 (11.4)
Noise of the monitor was disturbing to me	91 (15.1)	71 (11.8)	102 (16.9)	339 (56.2)
Noise of the monitor disturb others	67 (11.1)	24 (4.0)	43 (7.1)	469 (77.8)
Monitor was embarrassing to wear	212 (35.2)	10 (1.7)	93 (15.4)	288 (47.8)

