**D.11.5.1. Hypothesis 2a: Sleep BP on HBPM will provide an accurate estimate of sleep BP on ABPM.**

We will assemble a scatterplot of mean sleep SBP on HBPM versus ABPM and a intraclass correlation coefficient will be calculated. The statistical significance of the difference in mean sleep SBP on HBPM versus ABPM will be calculated using paired t-tests. The analysis will be repeated using sleep DBP on HBPM versus ABPM. We will create Bland-Altman plots showing the difference between sleep BP on HBPM versus ABPM by ABPM sleep BP level. We will calculate the percentage of participants who have a 10 mm Hg or larger absolute difference in their mean sleep SBP or a 5 mm Hg or larger absolute difference in their mean sleep DBP when measured by HBPM versus ABPM. Differences in mean sleep BP (SBP and DBP, separately) measured on HBPM versus ABPM will be calculated within age, race/ethnicity and sex sub-groupings. We will calculate the overall agreement and Kappa statistic between nocturnal hypertension on HBPM and ABPM, and test for a difference in prevalence using McNemar's test. We will compare differences in mean sleep SBP and DBP by randomization assignment using t-tests. If differences are statistically significant, analyses will include adjustment for randomization assignment.

**D.11.5.2. Hypothesis 2b: HBPM will be better tolerated than ABPM.** An overall score on the HBPM/ABPM tolerability questionnaire will be calculated by summing the scores on the eight Likert-type items after reverse coding positively-framed items (i.e., those with higher scores indicating better tolerability). Consistent with the approach of Viera, poor tolerance will be defined as an overall score  $\geq 75^{\text{th}}$  percentile on the results for ABPM. The cut-point identified for ABPM will be applied to define poor HBPM tolerability. Also, the percent of participants who report "pain", "skin irritation" and "bruising" from the ABPM device, and separately, the HBPM device will be calculated. The statistical significance of differences in responses to these items when wearing the HBPM and ABPM devices will be calculated using McNemar tests.

**D.11.6. Aim 3. Compare the associations of unattended versus attended clinic BP, unattended clinic BP versus awake BP on ABPM, and sleep BP on HBPM versus ABPM with two markers of end-organ damage, LVMI and ACR.**

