**Hypothesis 3a:** The association with end-organ damage will be stronger for unattended vs. attended clinic BP.

**Hypothesis 3b:** The association with end-organ damage will be similar for unattended clinic and awake BP.

**Hypothesis 3c:** The association with end-organ damage will be similar for sleep BP by HBPM and ABPM.

Below we describe the analysis plan for testing Hypothesis 3a. The analysis plan will be identical for Hypotheses 3b and 3c. We will calculate the intraclass correlation coefficients between (1) attended clinic BP and (2) unattended clinic BP with LVMI. The statistical significance of the difference in the correlation coefficients will be calculated using the Fisher r-to-z transformation accounting for the within-person correlation between unattended and attended BP measurements. Also, the association between clinic BP, measured unattended and attended, separately, and LVMI will be calculated using linear regression. For these models, clinic BP will be modeled in categories, using restricted quadratic splines, and, if appropriate, as a continuous variable (e.g., per 10 mm Hg higher SBP). Two levels of adjustment will be performed as described in **Section D.11.2.**

For secondary testing of Hypothesis 3, we will model the outcome of LVH defined as an  $\text{LVMI} \geq 96 \text{ g/m}^2$  in women and  $\text{LVMI} \geq 116 \text{ g/m}^2$  in men using Poisson regression with robust standard errors and two levels of adjustment (**Section D.11.2**). The analyses will be repeated for the outcome of the ACR. When modeled as a continuous variable, ACR will be log-transformed due to its skewed distribution. As a dichotomous variable, albuminuria will be defined as an sex/race-adjusted  $\text{ACR} > 25 \text{ mg/g}$ .

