#### D.12.1.1. Sample size considerations for hypothesis 1a.

**Figure 4** shows the minimal detectable difference in differences with awake ABPM comparing unattended vs attended clinic BP. With 600 participants we can detect that the absolute difference with awake ABPM is 1.5 and 1.2 mm Hg smaller for unattended vs attended clinic BP assuming a correlation of 0.5 and 0.7, respectively between clinic BP and awake BP on ABPM. In a sub-group of 160 participants (e.g., African Americans), we can detect that the absolute difference with awake ABPM is 3.1 and 2.4 mm Hg smaller for unattended vs. attended clinic BP.

Smaller absolute differences can be detected if the correlation between attended and awake BP is higher.

**D.12.1.2. Sample size considerations for hypothesis 1b.** If 85% of participants have the same concordance/discordance status for both comparisons (i.e., attended clinic hypertension versus awake hypertension and unattended clinic hypertension versus awake hypertension), enrollment of 600 participants will provide 80% statistical power to detect a difference of 5% in the two overall agreements (e.g., 70% vs. 75%). If the expected agreement is 50%, we will have an 80% statistical power to detect a difference between Kappa statistics of 0.4 and 0.5 using a two-sided alpha level of 0.05. With 600 participants and a phenotype prevalence of 15%, we can detect a difference in the prevalence of 4% when clinic BP is measured unattended versus attended. In a sub-group of 160 participants, we can detect a difference of 8%. Based on these estimates, we chose to enroll 630 participants in the proposed study (n=600 with complete data).

#### D.12.2. Aim 2

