**D.12.2.1. Minimum detectable effect size - hypothesis 2a.** We assumed a standard deviation of sleep SBP of 15 mm Hg and sleep DBP of 10 mm Hg when measured using ABPM and HBPM. Also, the correlation between sleep BP on ABPM and HBPM was assumed to be 0.5 for SBP and DBP. For this analysis, we are testing that mean sleep BP is equivalent when measured by HBPM and ABPM. A sample size of 600 participants will provide 80% statistical power to exclude an absolute mean difference equal to or larger than 2.1 mmHg for SBP or 1.4 mmHg for DBP comparing ABPM versus HBPM exists. In a sub-group of 160 participants, we can exclude an absolute mean difference equal to or larger than 4.0 mmHg for SBP or 2.7 mmHg for DBP. If the correlation of sleep BP on ABPM and HBPM is higher (e.g., 0.7 or 0.9), we can exclude smaller absolute differences. A sample size of 600 participants will provide narrow confidence intervals for the observed agreement and kappa statistic for nocturnal hypertension comparing HBPM and ABPM. For example, the 95% confidence interval for an observed agreement of 80% and 90% would be 77%-83% and 88%-92%, respectively, and for a kappa statistic of 0.6 and 0.8 would be 0.54-0.66 and 0.75-0.85, respectively.

**D.12.2.2. Minimum detectable effect size - hypothesis 2b.** By definition, 25% of participants will have poor tolerance to ABPM. The minimum detectable difference in the prevalence of poor tolerance comparing HBPM versus ABPM depends on the percentage of participants who have poor tolerance to one method but not to the other. With a sample size of 600 participants, we can detect a difference in poor tolerance of ABPM and HBPM of 3% (25% versus 22%) if 20% of participants report poor tolerance to both methods (e.g., if 5% has poor tolerance to ABPM but not to HBPM, and 2% has poor tolerance to HBPM but not to ABPM). Assuming 5% of participants experience bruising with both ABPM and HBPM, we will have 80% power to detect a difference in the prevalence of bruising of 3% or larger comparing ABPM and HBPM.

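### The Analysis Plan and D.11.5.1/D.11.6 differ with no stated precedence; followed as written, the Analysis Plan never compares Aim 3's associations, leaves ACR untransformed and reports Hypothesis 2a against zero difference

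*Combined protocol and SAP*

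**What the plan says.** **Hypothesis 2a.** D.12.2.1 states: "For this analysis, we are testing that mean sleep BP is equivalent when measured by HBPM and ABPM". It adds that 600 participants give 80% power "to exclude an absolute mean difference equal to or larger than 2.1 mmHg for SBP or 1.4 mmHg for DBP". D.11.5.1 then says: "The statistical significance of the difference in mean sleep SBP on HBPM versus ABPM will be calculated using paired t-tests". Around that test it plans an intraclass correlation, Bland-Altman plots, the share of participants differing by at least 10 mm Hg SBP or 5 mm Hg DBP, and agreement, kappa and McNemar's test for nocturnal hypertension. It also plans subgroup differences and a comparison by device order, with this rule: "If differences are statistically significant, analyses will include adjustment for randomization assignment". Item 5 of the Analysis Plan keeps the means and, in 5b, one instruction for the comparison: "Calculate the absolute mean difference with 95% confidence intervals for ABPM vs. HBPM, using a paired T-test". The P-value column of its Table 7 is for a difference of zero.

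**Aim 3.** D.11.6 plans a Fisher r-to-z test of the difference between two dependent correlations, regression at the two adjustment levels of D.11.2, and log-transformed ACR when ACR is continuous. That scheme is written for 3a (stronger) and carried over to 3b and 3c (similar): "The analysis plan will be identical for Hypotheses 3b and 3c". Items 7 to 12 of the Analysis Plan fit one BP measure at a time, name no covariates and give no contrast between measures. The ACR tables (12 to 14) are in mg/g, and the footnotes to Tables 12 and 14 describe ACR only as a continuous variable.

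**The concern.** Aim 3 sets out to compare associations. Two slopes in adjacent rows, each with its own P-value against zero, do not compare them: both can be significant and still differ, or one can miss significance with no real difference. The reader is left to judge stronger or similar by eye. For 3b and 3c, even the D.11.6 test looks only for a difference, and a non-significant result would not by itself show similarity.

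For 2a, a P-value against zero cannot separate a trivial mean difference from an important one. A mean difference also says little about how far HBPM is from ABPM in one person, which is what the agreement analyses in D.11.5.1 address. D.13.4 rests diagnosis without ABPM on Aims 1 and 2 being confirmed, so the meaning of accurate matters. Table 3 of the research plan faults prior studies for not reporting agreement on nocturnal hypertension. Item 5 omits that analysis, and the Analysis Plan's data-management section creates no nocturnal hypertension variable.

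**Working it through.** **1. The plan's own figures.** D.12.2.1 assumes SDs of 15 and 10 mm Hg and a correlation of 0.5, so the SD of the paired difference is SD × √(2 × 0.5) = 15 and 10. For a rule that the 95% CI lies inside the limit, with 80% power at a true difference of zero, the limit is SD/√600 × (1.960 + 1.282): 1.99 and 1.32 mm Hg. The stated 2.1 and 1.4 are slightly conservative, and nothing below depends on the gap. For D.12.3 at n = 600, a dependent-correlation test gives 0.106/0.091/0.080 and 0.083/0.073/0.066, matching the stated 0.11/0.09/0.08 and 0.08/0.07/0.07.

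**2. Hypothesis 2a** (Analysis Plan Table 7, N = 547). The reported differences, ABPM minus HBPM, are -2.3 (-3.0 to -1.5) SBP and -1.9 (-2.5 to -1.4) DBP. Neither interval lies within ±2.1 or ±1.4. The zero-difference test (P < .0001) points the same way.

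**3. Individual agreement.** SD of differences = CI half-width / 1.964 × √547.
- SBP: 0.75/1.964 × 23.39 = 8.93 (8.3 to 9.5 allowing for rounding).
- DBP: 0.55/1.964 × 23.39 = 6.55 (6.0 to 7.1).

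Under normality, P(|D| ≥ 10) for SBP is 28% (25 to 31%) and P(|D| ≥ 5) for DBP is 46% (42 to 50%). The ranges cover rounding of the SD only, not sampling error or non-normality.

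**4. Device order** (Table 1 means, HBPM minus ABPM).
- SBP: ABPM first 105.7 - 104.7 = 1.0; HBPM first 106.9 - 103.4 = 3.5; gap 2.5. SE = 8.93 × √(1/273 + 1/274) = 0.76, z = 3.27, 95% CI about 1.0 to 4.0, P about 0.001.
- DBP: 61.8 - 60.4 = 1.4 against 62.9 - 60.1 = 2.8; gap 1.4, SE 0.56, z = 2.50, P about 0.01.

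This assumes that the 547 split about evenly by order and that Table 1 means stand in for the paired set (overall SBP gap 106.3 - 104.1 = 2.2, against 2.3 paired).

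**5. The comparison missing from Aim 3** (LVMI, unadjusted). Each correlation is r = t/√(t² + n - 2), from the t-statistics in Tables 9 to 11. The correlation between two BP measures is (s₁² + s₂² - s_d²)/(2s₁s₂), from the SDs and CIs in Tables 2 and 7. Intervals use Zou's method.

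| Contrast (first minus second) | n | r, first | r, second | r between measures | Difference (95% CI) |
|---|---|---|---|---|---|
| 3a SBP, unattended - attended | 587 | 0.296 | 0.298 | 0.95 | -0.002 (-0.03 to 0.02) |
| 3a DBP | 587 | 0.165 | 0.189 | 0.94 | -0.024 (-0.052 to 0.003) |
| 3b SBP, awake - unattended | 554 | 0.347 | 0.300 | 0.76 | 0.047 (-0.007 to 0.10) |
| 3b DBP | 554 | 0.182 | 0.167 | 0.69 | 0.015 (-0.050 to 0.080) |
| 3c SBP, ABPM - HBPM | 533 | 0.277 | 0.211 | 0.67 | 0.065 (-0.001 to 0.131) |
| 3c DBP | 533 | 0.156 | 0.110 | 0.66 | 0.046 (-0.023 to 0.116) |

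For 3c SBP, varying the between-measure correlation from 0.62 to 0.72 moves the interval from (-0.006 to 0.137) to (0.004 to 0.127), with P from 0.07 to 0.04. For 3a DBP, P is about 0.08 from the t-statistics and about 0.03 from the rounded standardised betas.

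**The case against.** The strongest reply is that nothing has been removed. No text says that the Analysis Plan replaces D.11, and D.11.5.1 and D.11.6 still stand. The Analysis Plan can be read as a list of tables to program. The D sections, for their part, read like an earlier proposal: they name Omron and SpaceLabs devices and fasting blood, where the manual has Microlife devices and a non-fasting draw. This stands. A reader might infer that the sponsor has abandoned the D.11 analyses, but the documents show only two differing texts with no order of precedence.

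Four other readings go too far.
- Device order is ignored. It is not: Table 1 shows sleep BP on both devices by order. What is missing is the formal test and adjustment. Because the sequences are balanced, adjustment would change the overall mean difference little.
- HBPM failed a pre-set equivalence limit. D.12.2.1 gives 2.1 and 1.4 mm Hg as differences that can be excluded, not as acceptance limits, and D.12.1.2 sets enrolment from the Aim 1 estimates.
- The zero-difference test gave a wrong answer for 2a. Item 5b also provides a 95% CI, which allows an equivalence reading, and no conclusion is reversed.
- The unattended DBP slope on ACR (-0.37 at n = 555 in Table 12, -0.09 at n = 523 in Table 13) shows the effect of omitting the log. Those are different samples and do not measure that effect.

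It is also fair to say that D.11.5.1 plans several measures of agreement, so a single pass/fail rule for accurate is partly a matter of preference.

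**Conclusion.** The concern holds as a conflict between two texts that must be reconciled before the results are reported. The textual gaps are certain: the Analysis Plan contains no estimate of a difference between associations, no D.11.2 adjustment, no log-transformed ACR, and for 2a neither the individual-level agreement analyses nor a formal order test.

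The sizes are less certain. The agreement shares and the order gap rest on rounded summaries, normality for the former and a near-even split for the latter. On those assumptions, the D.11.5.1 rule for adjusting by order would very likely be triggered. The Aim 3 differences are unadjusted and indicative only. SBP 3c is borderline and cannot be called from rounded tables, and DBP 3a is close to zero and runs against the hypothesis. The missing criterion for accurate leaves 2a without an agreed reading. Since the tables already hold results, a criterion could now be set only post hoc.

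**What to change.** 1. State which text governs, and reconcile the Analysis Plan with D.11.5.1 and D.11.6.
2. In items 7 to 12, add the difference between the two dependent correlations (or standardised betas) with a 95% CI by Zou's method or bootstrap. Give it unadjusted and at the two D.11.2 levels, using the covariates actually collected and stating deviations. The second level needs stress and anxiety: the Visit 1 form names Perceived Stress but the REDCap instrument lists hold no stress instrument, and anxiety is collected only in the supplement. State the sign convention. Report 3b and 3c as estimates with CIs, and do not read non-significance as similarity.
3. Use log-transformed ACR in items 10 to 12.
4. For 2a, do not use the zero-difference P-value as the test of accuracy. Report the planned 95% CI beside 2.1 and 1.4 mm Hg, labelled as planning figures and not acceptance limits. Call any pass/fail rule added now post hoc, unless the plan posted under D.15 contains one.
5. Add to item 5 the intraclass correlation, Bland-Altman plots, the 10/5 mm Hg shares and nocturnal hypertension agreement with kappa and McNemar's test. Put device order in the sleep BP model directly, without a significance pre-test.
6. Treat race/ethnicity subgroups as descriptive: Table 1 has 39 Hispanic participants, against at least 160 planned in D.4.2.

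The cost is more analysis on existing data, with accuracy and similarity becoming harder to claim.

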## 6. Did the noise of the monitor disturb others?

7. Did you find the monitor embarrassing to wear?

8. Did you find the monitor interfered with your normal sleeping pattern?

No Yes

9a. If you answered 'Yes' to Q8, how much was your sleep disturbed?

A little A moderate amount A lot

9b. If your sleep was disturbed, did the monitor wake you up after you had fallen asleep?

No Yes

10. Did the monitor disturb you so much during the night that you removed it?

No Yes

11. How much pain did you experience while wearing the monitor?

None A little A moderate amount A lot

12. How much irritation did you experience while wearing the monitor?

None A little A moderate amount A lot

13. How much bruising did you experience while wearing the monitor?

None A little A moderate amount A lot

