### **Aims and hypotheses**

**Primary Aim 1:** To examine whether measuring unattended clinic BP with an automated device will provide a more accurate estimate of awake BP on ABPM than measuring attended clinic BP with an automated device.

**Hypothesis 1a:** The absolute difference with awake BP will be smaller for unattended vs. attended clinic BP.

**Hypothesis 1b:** The agreement between hypertension status using BP measured in the clinic and on ABPM while awake will be higher when clinic BP is measured unattended vs. attended. Also, the prevalence of both white coat and masked hypertension will be lower when measuring unattended clinic BP.

**Primary Aim 2:** To examine whether a new HBPM device provides an accurate approach for measuring sleep BP.

**Hypothesis 2a:** Sleep BP on HBPM will provide an accurate estimate of sleep BP on ABPM.

**Hypothesis 2b:** HBPM will be better tolerated (e.g., less awakening during sleep, pain, bruising) than ABPM.

**Primary Aim 3:** To compare the associations of unattended versus attending clinic BP, unattended clinic BP versus awake BP on ABPM, and sleep BP on HBPM versus ABPM with two markers of end-organ damage, left ventricular mass index (LVMI) and urinary albumin-to-creatinine ratio (ACR).

**Hypothesis 3a:** The association with end-organ damage will be stronger for unattended vs. attended clinic BP.

**Hypothesis 3b:** The association with end-organ damage will be similar for unattended clinic BP and awake BP.

**Hypothesis 3c:** The association with end-organ damage will be similar for sleep BP by HBPM and ABPM.

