**D.8.4.3. Sleep HBPM and Actigraphy.** The participant will be given a sleep HBPM device (HEM-7080IC, Omron, Bannockburn, IL, USA) with appropriate-sized cuff and instructed in how to put on the cuff and use the monitor properly. Participants will be instructed to put the HBPM device on the same arm used for all other study procedures, the evening they leave the clinic visit. They will also be fitted with an Actiwatch activity monitor on their wrist to wear during the HBPM period. Participants will be instructed to put on the HBPM device before going to bed and to keep it on until they wake up in the morning (i.e., after 5am). The device will be programmed to take 3 readings, at 2am, 3am, and 4am. Participants will be trained to fill out the HBPM Device Log, which documents sleep and awake times. BP readings on the HBPM will not be visible to participants. One night of sleep HBPM will be conducted.

**D.8.5. Tolerability of ABPM and HBPM.** Tolerability for undergoing ABPM and HBPM will be assessed using a 15-item questionnaire. This questionnaire has items assessing the comfort with wearing the devices and

disturbances resulting from completing ABPM and HBPM. Additionally, there are questions on pain, skin irritation and bruising resulting from wearing the devices. Eight of the questions are answered with a Likert-type scale (e.g., Did you find the monitor interfered with your normal sleeping pattern? With response options of 0 “Not at all”, 5 “Somewhat”, 10 “Extremely”). The remaining 7 questions have response options of “yes” or “no” (e.g., “Did you experience pain from wearing the monitor?”).

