**D.12. Sample size/minimum detectable effects.**

[figure not shown]
**D.12.1. Aim 1.** Sample size and minimal detectable difference calculations were based on 80% statistical power and a two-sided alpha level of 5%. These calculations were performed using simulations and R version

3.3.2. We estimate that a sample size of 600 participants (630 enrolled participants with 30 participants [5%] not completing the study) will allow us to detect small but clinically relevant differences for each aim.

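### SAP item 6 only describes tolerability; it omits the poor-tolerance endpoint, the McNemar tests and the awakening item that Hypothesis 2b rests on

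*Combined protocol and SAP*

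**What the plan says.** The SAP's Aims and hypotheses make Hypothesis 2b directional: "HBPM will be better tolerated (e.g., less awakening during sleep, pain, bruising) than ABPM". Objective 5 is only to determine the tolerability of the two devices. Statistical analysis item 6 then reads "Calculate the number and percentage of side effects and tolerability", split into ABPM only, HBPM only, both and neither. Table 8 (N = 603) has 12 rows of such counts and no inferential column.

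The research plan in the same combined document goes further. D.11.5.2 states: "An overall score on the HBPM/ABPM tolerability questionnaire will be calculated by summing the scores on the eight Likert-type items", with positively framed items reverse-coded. Poor tolerance is a score at or above the ABPM 75th percentile, and the same cut is applied to HBPM. McNemar tests are named in the sentence that follows the one on pain, skin irritation and bruising. D.12.2.2 gives detectable differences for poor tolerance and for bruising.

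D.8.5 describes a 15-item questionnaire: "Eight of the questions are answered with a Likert-type scale". Its example of such an item is interference with normal sleep, and its example of a yes/no item is pain. Both device forms carry item 9b: "If your sleep was disturbed, did the monitor wake you up after you had fallen asleep".

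**The concern.** Aim 2 is a primary aim, and Hypothesis 2b is one of its two hypotheses. An analyst who follows item 6 to the letter produces percentages and no inference on it. The other SAP items for Aims 1 and 2 each ask for an interval, a test or a p-value (items 2b, 3a to 3i, 4a to 4c and 5b), so item 6 is the exception.

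Three things are lost: the endpoint that D.12.2.2 powers, the tests planned for the side effects, and awakening. Without paired differences, a reader of Table 8 cannot tell rows with a large, precise difference from rows with little or none. One positively framed row, straightforward to use, is printed among negatively framed ones, so an excess for ABPM can be misread as a disadvantage of ABPM.

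**Working it through.** **1. The plan's own power figure.** Inputs from D.12.1 and D.12.2.2: n = 600, two-sided alpha 5%, power 80%, 5% poor tolerance with ABPM only and 2% with HBPM only. So ψ = 0.05 + 0.02 = 0.07 and d = 0.05 − 0.02 = 0.03. For a paired (McNemar) comparison:

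n = [1.960·√ψ + 0.842·√(ψ − d²)]² / d² = [1.960·0.2646 + 0.842·0.2629]² / 0.0009 ≈ 608.

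Power at n = 600 is Φ[(0.03·√600 − 1.960·0.2646) / 0.2629] ≈ 79.5%. The stated figure reproduces, and it belongs to an endpoint that item 6 does not contain. The bruising statement gives no discordant split. It reproduces at about 7% total discordance (79.5%); power would be 91% at 5% and 64% at 10%.

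**2. Planned against written.**

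| Element | Research plan | SAP item 6 / Table 8 |
|---|---|---|
| Poor-tolerance score, ABPM 75th-percentile cut | D.11.5.2, powered in D.12.2.2 | Absent |
| McNemar tests for pain, irritation, bruising | D.11.5.2 | Counts only |
| Awakening | Named in Hypothesis 2b; item 9b on both forms | No row |

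**3. What the printed counts give.** With b = ABPM only, c = HBPM only and n = 603 (every row sums to 603): difference = (b − c)/n; χ² = (b − c)²/(b + c); standard error = √[(b + c) − (b − c)²/n]/n. For pain, (160 − 37)/603 = 20.4 points and χ² = 123²/197 = 76.8. Differences below are ABPM minus HBPM.

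| Row | b | c | Points (95% CI) | p |
|---|---|---|---|---|
| Pain | 160 | 37 | 20.4 (16.1, 24.7) | 1.9×10⁻¹⁸ |
| Irritation | 178 | 26 | 25.2 (21.0, 29.4) | 1.9×10⁻²⁶ |
| Bruising | 84 | 19 | 10.8 (7.6, 14.0) | 1.5×10⁻¹⁰ |
| Interfered with sleep | 124 | 56 | 11.3 (7.0, 15.5) | 4×10⁻⁷ |
| Uncomfortable | 109 | 68 | 6.8 (2.5, 11.1) | 0.002 |
| Noise to self | 91 | 71 | 3.3 (−0.8, 7.4) | 0.12 |
| Removed during sleep | 23 | 23 | 0.0 (−2.2, 2.2) | 1.0 |
| Straightforward to use, as printed | 12 | 6 | 1.0 (−0.4, 2.4) | 0.16; exact 0.24 |

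The other four rows (heavy, cumbersome, noise to others, embarrassing) differ by 12.6, 17.1, 7.1 and 33.5 points, each with p < 10⁻⁵. Nine of 12 rows therefore favour HBPM significantly. The straightforward row is positively framed, so 12 against 6 leans toward ABPM.

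**4. Awakening.** Item 9b follows the yes/no interference question (Q8). If a No to Q8 counts as not woken, Table 8 gives only ceilings: at most 124 + 219 = 343 woken with ABPM (56.9%) and 56 + 219 = 275 with HBPM (45.6%). The 9b difference itself cannot be recovered from the table.

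**5. Forms against definition.** The HBPM form has seven items on a scale from not at all to a lot. It then asks interference as No/Yes, with a graded follow-up (9a), and grades pain, irritation and bruising in four levels. D.8.5 has these the other way round: interference is a Likert example and pain a yes/no example. From the visible forms, the eight-item score cannot be built exactly as D.8.5 and D.11.5.2 define it.

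**The case against.** The strongest reply is that nothing in item 6 says it replaces D.11.5.2. The score, tests and power statement still stand in the same document, and the four paired cells hold all that an item-level McNemar test needs. That is fair: the defect is two unreconciled plans, and the item-level part can be repaired from print. It does not cover the score or item 9b, which need participant-level data.

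Awakening is also partly represented by the sleep-interference row, its parent question. But that is a different question, and step 4 shows that it only bounds the answer.

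Some stronger readings are tempting, and the documents do not support them:

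- A reader might infer that no tolerability score can be computed at all. The opening items of the ABPM form and most response scales do not appear in the public text, and a graded eight-item score (Q1 to Q7 plus Q8 and 9a combined) looks possible.
- A reader might take the score to be the main outcome. D.11.5.2 never says so; it is a powered outcome.
- A reader might take McNemar tests to have been planned for all 12 rows. The sentence most naturally covers pain, skin irritation and bruising.

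**Conclusion.** The point stands in this form: item 6 is descriptive only and does not carry out the Hypothesis 2b analysis that D.11.5.2 plans and D.12.2.2 powers, and it has no awakening row. The score definition and the fielded HBPM form also disagree and must be reconciled.

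The effect on the side-effect conclusion is probably small, since pain, irritation and bruising favour HBPM at p < 10⁻⁹. A reader might infer from noise to self, removal during sleep and straightforward to use that the devices are equal on those items. The data do not show that. Noise to self is compatible with anything from a 0.8-point disadvantage to a 7.4-point benefit of HBPM, and 578 of 603 found both devices straightforward. These rows show no significant benefit, and no more. The overall poor-tolerance comparison and awakening remain unknown.

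The recalculation takes the Table 8 cells as printed, including their split of graded answers into occurred or not, for which item 6 states no rule.

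**What to change.** Revise SAP item 6 and Table 8 as follows.

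1. For pain, irritation and bruising, report the paired ABPM-minus-HBPM difference with 95% CI and the McNemar p-value (exact when discordant counts are small), as D.11.5.2 planned. For the other rows, give paired differences with CIs as supportive, with straightforward to use reverse-coded.
2. Add a row for item 9b with its paired difference and CI. Count participants who answered No to Q8 as not woken, and those with no Q8 answer as missing.
3. Restore the poor-tolerance endpoint with the ABPM 75th-percentile cut and a paired test, after reconciling the score with the fielded forms, for example Q1 to Q7 plus Q8 and 9a combined.
4. Label any departure from D.11.5.2, including a changed score, as made after Table 8 was seen.

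The cost is SAP wording and one revised table. The tests in (1) follow from the printed counts; (2) and (3) use questionnaire data already collected.
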